6.5 Subject Disposition

Randomized

Individuals are considered randomized if they have been assigned a randomization number. Randomized individuals are referred to as “subjects”.

Completing the Double-Blind Treatment Phase

Subjects are defined as completing the DBTP if they complete week 24 assessment. It will be derived from the End of Double-Blind Treatment Phase CRF page with “Completed” as the reason for ending study phase.

Completing the Open-Label Treatment Phase

Subjects are defined as completing the OLTP if they complete the week 76 assessment. It will be derived from the End of Open-Label Treatment Phase CRF page with “Completed” as the reason for ending study phase.

Completing Study

Subjects are defined as completing study if they complete the whole 88 weeks of study evaluation. It will be derived from the End of Study CRF page with “Completed” as the primary reason for ending study.

Exposed to Investigational Product

Subjects are defined as exposed if they receive at least one dose of investigational product.

Completing the Double-Blind Investigational Product

Subjects are defined as completing double-blind investigational product if they complete week 20 IP dose or temporarily withhold IP at week 20 and continue to receive IP during OLTP. It will be derived from the End of IP DBTP CRF page with “Completed” as the reason for ending IP.

Completing the Open-Label Investigational Product

Subjects are defined as completing open-label investigational product if they complete week 72 IP dose. It will be derived from the End of IP OLTP CRF page with “Completed” as the reason for ending IP.

On-study

Subjects are considered on-study if they have been randomized and have not yet had their end of study visit.

6.6 Arithmetic Calculations

Duration of Migraine

The number of years from the diagnosis date (DXDT) of migraine (migraine with aura or migraine without aura, whichever is earlier) to the date informed consent is signed.

If month or day of the diagnosis date is missing, follow the formula below to calculate the duration:

Observed portion	Missing portion	Formula to Calculate Duration
Year, Month, Day		(Informed Consent Day – DXDT)/365.25
Year, Month	Day	[Year(Informed Consent Day)-Year(DXDT)]+ [Month(Informed Consent Day)-Month(DXDT)]/12 *if it equals 0, add 1 month or 1/12 years (this is to avoid a disease duration of 0)
Year	Month, Day	[Year(Informed Consent Day)-Year(DXDT)] *if it equals 0, add 1 month or 1/12 years (this is to avoid a disease duration of 0)

Duration of DB IP Exposure

If subject enter into OL treatment phase,

Duration = Minimum (Last DB Dose Date + 27, First OL Dose Date - 1, EOS Date) – First DB Dose Date + 1

Otherwise,

Minimum (Last DB Dose Date + 27, EOS Date) – First DB Dose Date + 1

Duration of OLTP IP Exposure

Minimum (Last OLTP Dose Date + 27, EOS Date, Date of Data Cut-off) – First OLTP Dose Date + 1

Change from Baseline in Monthly Efficacy Measurement

The change from baseline in monthly efficacy measurement is the monthly efficacy measurement prior to the given time point minus the baseline monthly efficacy measurement. Please refer to the Monthly Intervals defined in [Section 6.4](#). For example, change from baseline in monthly migraine days at Week 24 will be calculated based on the following:

$$(\text{Monthly migraine days during the week 24 interval}) - (\text{monthly migraine days during the baseline phase})$$

If the baseline or post-baseline value is missing, then the change from baseline is set to missing.

Following Efficacy endpoints will be calculated as above:

- Change from baseline in monthly migraine days
- Change from baseline in monthly migraine attacks
- Change from baseline in monthly headache days
- Change from baseline in monthly migraine days with severe pain
- Change from baseline in monthly cumulative migraine hours
- Change from baseline in monthly cumulative migraine hours with severe pain
- Change from baseline in monthly acute medication use in days
- Change from baseline in monthly migraine-specific medication use in days
- Change from baseline in monthly average severity of migraine pain
- Change from baseline in monthly average migraine symptoms interference scale
- Change from baseline in monthly bed days due to migraine related symptoms
- Change from baseline in monthly missed work/school days due to migraine related symptoms
- Change from baseline in monthly headache impact scores as measured by HIT-6

Mean Change from Baseline in Monthly Efficacy Measurement over multiple months

The Mean Change from Baseline in Monthly Efficacy Measurement is the Arithmetic mean of each change from baseline value for the months considered

Percent Change from Baseline

The change from baseline divided by baseline and multiplied by 100:

$$(\text{Post-baseline} - \text{Baseline}) * 100 / \text{Baseline}$$

If the baseline value is 0 and the post-baseline value is also 0, then the percent change from baseline is set to 0. If the baseline value is 0 and the post-baseline value is non-zero, then the percent change from baseline is set to missing.

Percent change from baseline in (mean) monthly migraine days which is used to determine 50%, 75%, and 100% responder will be calculated as above.

Subject Incidence

The subject incidence for a given event in a given period is defined as the number of subjects with at least one reported occurrence of the event divided by the number of subjects who entered that period. For subjects with multiple occurrences of the same event, the event will only be counted once per subject.

Exposure-Adjusted Incidence Rate

The exposure-adjusted incidence rate for a given event in a given period is defined as the number of subjects with at least one reported occurrence of the event in a given time period at risk divided by total exposure time of all subjects who are at risk for the event.

For subjects with events, only the time until the first event contributes to the total exposure time. For subjects with no event, the exposure time is the time from the first IP dose to the last follow-up assessment. This rate will be presented per 100 subject years. For subjects with multiple occurrences of the same event, the first occurrence of an event will be counted for each subject.

6.7 Disease Characteristics

Migraine-Specific Medications

Migraine-specific medications include two categories of medications: triptan-based and ergotamine-based migraine medications collected from subject's eDiary.

Treatment Failure of Prior Migraine Prophylactic Medications

Treatment failure of prior migraine prophylactic medications is determined by “Reason for ending medication” as “Lack of efficacy” or “Adverse Reaction” in the Prior Migraine Prophylactic Medication eCRF page.

7. Analysis Subsets

7.1 Full Analysis Set

The Full Analysis Set (FAS) includes all subjects who were randomized in the study. Subjects will be analyzed according to their randomized treatment, regardless of the treatment received. Tabulations of demographic and baseline characteristics, disposition, and important protocol deviations (IPD) will utilize this analysis set.

7.2 Efficacy Analysis Set

The Efficacy Analysis Set (EAS) will be used to carry out the primary analyses of efficacy endpoints, which is a subset of the Full Analysis Set consisting of subjects who received at least one dose of IP and completed at least one post-baseline monthly migraine day measurement in the DBTP. Subjects will be analyzed according to their randomized treatment, regardless of the treatment received. Analyses for efficacy endpoints and patient reported outcomes (PROs) will utilize this analysis set.

7.3 Safety Analysis Set

The Safety Analysis Set will consist of all randomized subjects who received at least one dose of IP. Subjects will be analyzed according to the randomized treatment unless a subject has received the incorrect dose during the entire DBTP. Analyses for safety endpoints and summary of IP administration in DBTP will utilize this analysis set.

7.4 Open-Label Treatment Phase Set

The Open-Label Treatment Phase Set (OLTPS) will consist of all subjects receiving at least one dose of AMG 334 in the OLTP. This analysis set will be used when summarizing data collected during the OLTP.

7.5 Per Protocol Set

The Per Protocol Set is a subset of the Efficacy Analysis Set which consists of subjects who received IP at Week 12, 16, and 20 and do not satisfy any of the following conditions:

- 1) Important protocol deviations that will potentially impact primary analysis of efficacy endpoints from week 16 to week 24 or violate GCP at site as specified in the IPD List ([Cabinets/AMG 334/TMF/20120309 - Episodic Migraine Prophylaxis](#))

Japan/Study Protocol Compliance/Protocol Deviation Listing) to be applied in per protocol analysis:

- Informed Consent was not provided
 - Monthly migraine days at baseline is < 4 or \geq 15
 - Monthly headache days at baseline is \geq 15
 - No therapeutic response with > 2 of the 7 medication categories for prophylactic treatment of migraine after an adequate therapeutic trial
 - Received botulinum toxin in the head and/or neck region within 4 months prior to the start of the baseline phase and throughout the study
 - Ergotamine-derivatives, steroids, and triptans used for migraine prophylaxis are excluded within 2 months prior to the start of the baseline phase and throughout the study
 - Devices and procedures used for migraine prophylaxis are excluded within 2 months prior to the start of the baseline phase and throughout the study
 - Using opioid- or butalbital-containing analgesics on \geq 4 days in any month during the 2 months prior to the start of the baseline phase
 - History of chronic pain syndromes (eg, fibromyalgia, chronic back pain, chronic pelvic pain)
 - Received current migraine prophylaxis medication prior to the start of the baseline phase after closure of the stratum
 - Received less than 75% or more than 125% of planned total dose of AMG 334 at any of the weeks 12, 16, 20 (based on unblinded information)
(Example: subject who was randomized to AMG 334 70 mg treatment group received 140 mg, not 70 mg at week 20)
 - Important GCP violation resulting in that data can't be used for analysis
- 2) In addition to above protocol deviations, subjects who did not have an observed monthly migraine day value at any of the weeks 16, 20, 24 will also be excluded from Per Protocol Set

The Per Protocol Set will be used to perform the sensitivity analysis on the primary and secondary efficacy endpoints.

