MCV	Mean corpuscular volume
mg	Milligram
MI	Multiple imputation
Migraine Attack	An episode of any qualified migraine headache. The following rules will be used to distinguish an attack of long duration from two attacks, or to distinguish between attacks and relapses: 
 a) A migraine attack that is interrupted by sleep, or temporarily remits, and then recurs within 48 hours (ie, ≤ 48 hours between the start of the migraine attack to the time of the recurrence) will be considered as one attack and not two. b) An attack treated successfully with medication but with relapse within 48 hours (ie, ≤ 48 hours between the start of the migraine attack to the time of the recurrence) will be considered as one attack.
Migraine Day	Any calendar day in which the subject experiences a qualified migraine headache (onset, continuation, or recurrence of the migraine headache). A qualified migraine headache is defined as a migraine with or without aura, lasting for ≥ 30 minutes, and meeting at least one of the following criteria (a and/or b): 
 a) ≥ 2 of the following pain features: 
 • Unilateral • Throbbing • Moderate to severe • Exacerbated with exercise/physical activity b) ≥ 1 of the following associated symptoms: 
 • Nausea and/or vomiting • Photophobia and phonophobia 
If the subject took a migraine-specific medication (ie, triptan or ergotamine) during aura or to treat headache on a calendar day, then it will be counted as a migraine day regardless of the duration and pain features/associated symptoms.

Migraine-specific medications	Triptans and ergotamine-derivatives
mL	Milliliter
MNAR	Missing not at random
Monthly Headache Days	Number of headache days in any 28-consecutive day interval relative to study day 1
Monthly Migraine Days	Number of migraine days in any 28-consecutive day interval relative to study day 1
ng	Nanogram
NOAEL	No observed adverse effect level
NSAID	Nonsteroidal anti-inflammatory drug
OLTP	Open-label treatment phase

Abbreviation or Term	Definition/Explanation
PC	Product complaint
PCR	Polymerase chain reaction
PD	Pharmacodynamic
PE	Physical examination
PET	Positron emission tomography
PFS	Pre-filled syringe
pg	Picogram
PGt	Pharmacogenetics
PK	Pharmacokinetic
pM	Picomolar

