4.1 Inclusion Criteria

Criteria to be Assessed Prior to Entering the Subject into the Initial Screening Phase and/or Baseline Phase:

- 101 Adults ≥ 20 to ≤ 65 years of age upon entry into screening
- 102 Provided informed consent prior to initiation of any study-specific activities/procedures
- 103 History of migraine (with or without aura) for ≥ 12 months prior to screening according to the IHS Classification ICHD-3 ([Headache Classification Committee of the International Headache Society, 2013](#)) based on medical records and/or patient self-report
- 104 Migraine frequency: ≥ 4 and < 15 migraine days per month on average across the 3 months prior to screening (refer to [Section 10.1.1.4](#) for definition of migraine day)
- 105 Headache (ie, migraine and non-migraine headache) frequency: < 15 headache days per month on average across the 3 months prior to screening (refer to [Section 10.1.1.4](#) for definition of headache day)

Criteria to be Assessed During the Baseline Phase and Confirmed Prior to Randomizing the Subject into the Double-blind Treatment Phase:

- 106 Migraine frequency: ≥ 4 and < 15 migraine days during the baseline phase based on the eDiary calculations
- 107 Headache frequency: < 15 headache days during the baseline phase based on the eDiary calculations
- 108 Demonstrated at least 80% compliance with the eDiary (for example, completing eDiary items for at least 23 out of 28 days during the baseline phase)

CHU Substudy:

- 109 **Subjects must have provided informed consent for the substudy. Subjects enrolling in the CHU substudy must have received open-label 140 mg AMG 334 for at least 1 dose.**

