7. STUDY PROCEDURES

Refer to the Schedule of Assessments ([Table 2 -Table 4](#)) for an outline of the procedures required at each study visit.

Refer to the applicable supplemental manuals (eg, laboratory, ECG) for detailed collection and handling procedures.

Allowable windows for visits are the following:

- Each study visit during the 24-week double-blind treatment phase and safety follow-up has a window of ± 3 consecutive calendar days.
- The day 1 visit (randomization day) has a window of 0, +7 consecutive calendar days; the day 1 visit must occur 28 to 35 days after the week -4 visit date.
- Each study visit during the 76-week **OLTP** has a window of ± 4 consecutive calendar days.
- All study visit target dates are to be calculated from the day 1 visit date.
- All study procedures for a given study visit are to be completed on the same day.
- Each PK substudy sampling has a window of ± 3 consecutive calendar days.

Refer to the Schedule of Assessments ([Table 4](#)) for an outline of the procedures required at each study visit in the CHU substudy.

Investigators are responsible for ensuring that all study procedures are performed as specified in the protocol.

Study visits should be conducted without additional non-protocol therapies and subjects should be reminded about the investigational nature of the study drug.

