9.3 Handling of Missing and Incomplete Data

Subjects may miss specific data points for a variety of causes. In general, data could be missing due to a subject's early withdrawal from study, a missed visit, or inability to evaluate an endpoint at a particular point in time. For this study, most of the efficacy endpoint will be collected via eDiary and subjects could miss entering several days of data in each monthly interval. The general procedures outlined below describe what will be performed when a data point is missing.

Missing eDiary data in the calculation of monthly measurements about subjects' migraine and non-migraine headaches will be handled using the following method.

1. For monthly intervals with ≥ 14 days of eDiary days (including retrospective eDiary days) in each interval:
 - a) Monthly frequency measurements (including migraine days, headache days, migraine attacks, cumulative hours of migraine headaches, acute medication use, bed days due to migraine and missed work/school days due to migraine) will be prorated to 28-day equivalents. Prorated result does not need to be rounded.
 - b) Monthly average severity of migraine pain, migraine related symptoms and monthly average scale of migraine interference with daily activity will calculated as the average of observed scores
2. For monthly intervals with < 14 days of eDiary use (including retrospective eDiary days), all monthly measurement will be set as missing and will be handled as described in [Section 9.3.3](#)

Missing eDiary data in the calculation of cumulative average monthly measurements about subjects' migraine and non-migraine headaches is treated as if subjects do not have headache or medication use to report.

Missing PROs (HIT-6) scheduled to be collected at office visit at certain assessment will not be imputed.

Missing safety endpoints will not be imputed. Missing day portion of AE start time will be imputed based on [Section 9.3.1](#).

Missing pharmacogenetic and antibody data will not be imputed.

Handling of missing or incomplete data for exposure-response analysis will be described in the E-R SSAP or associated documents to support population PK/PD dataset generation and E-R analysis.

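### SAP 7.5 re-tests the entry limits of 4 and 15 on a baseline prorated to 28 days, so subjects who met criteria 106 and 107 may be dropped from the Per Protocol Set

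*SAP*

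**What the plan says.** **Entry.** Protocol 4.1, criterion 106, requires "≥ 4 and < 15 migraine days during the baseline phase based on the eDiary calculations". Criterion 107 sets an upper limit of fewer than 15 on "headache days during the baseline phase based on the eDiary calculations". Criterion 108 asks for 80% diary compliance, with the example "completing eDiary items for at least 23 out of 28 days during the baseline phase". Criteria 104 and 105, on the three months before screening, are worded as monthly averages; 106 and 107 are not.

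**Length of the baseline phase.** Protocol section 7 says "the day 1 visit must occur 28 to 35 days after the week -4 visit date".

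**Analysis baseline.** SAP 6.1.1 runs the baseline period from the week -4 visit to the day before study day 1, with no cap at 28 days. It defines monthly migraine and headache days at baseline as the count in that period, with proration under 9.3. SAP 9.3 says that monthly frequency measures "will be prorated to 28-day equivalents. Prorated result does not need to be rounded", and 9.3.2 confirms that proration applies to baseline.

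**Re-test.** SAP 7.5 removes a subject from the Per Protocol Set as an important protocol deviator if "Monthly migraine days at baseline is < 4 or \geq 15", or if monthly headache days at baseline are 15 or more.

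**The concern.** The same cut-offs appear twice, but apparently on different quantities. Read literally, entry uses a count over whatever length the baseline phase had, while the deviation rule uses a rate per 28 days. Neither document says that the two figures are the same.

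A per-protocol analysis is meant to remove departures from the protocol. As written, it could instead remove subjects who satisfied every entry rule, picked out by where they sit on baseline frequency. That is also a covariate in the efficacy model (SAP 4.2). If the matter is left open, membership of the set would depend on how a programmer reads two bullets.

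**Working it through.** **The plan's own figure.** 0.80 × 28 = 22.4, so 23 diary days are needed in a 28-day phase (23/28 = 82.1%; 22/28 = 78.6%). This agrees with the example in criterion 108.

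**Inputs**
- Phase length L: 28 to 35 days (Protocol 7).
- Completed diary days d: from 0.80 × L, rounded up, to L (criterion 108, with the 80% applied to the actual length; this is an assumption for L above 28).
- Recorded days c: 4 to 14 for migraine, at most 14 for headache (criteria 106 and 107, read as raw counts; an assumption).
- SAP value v = c × 28 / d. SAP 9.3 gives the target of 28 days but not the formula; this is its natural reading.

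**Lower migraine limit.** v < 4 means d > 7c.
- c = 4: d must exceed 28. Results run from 4 × 28/29 = 3.86 to 4 × 28/35 = 3.20.
- c = 5: d must exceed 35, which cannot happen (5 × 28/35 = 4.00, which passes).

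Only subjects with exactly 4 days and 29 to 35 diary days fail.

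**Limit of 15, migraine or headache.** v ≥ 15 means d ≤ 28c/15.
- c = 14: d ≤ 26.1, so 26 or fewer. 14 × 28/26 = 15.08; 14 × 28/23 = 17.04.
- c = 13: d ≤ 24.3, so 24 or fewer. 13 × 28/24 = 15.17; 13 × 28/23 = 15.83.
- c = 12: d ≤ 22.4, which is below the 23-day minimum.

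| Phase length | Minimum diary days | Fails below 4 | Fails at 15 or more |
|---|---|---|---|
| 28 | 23 | none | 14 on 23–26; 13 on 23–24 |
| 29 | 24 | 4 on 29 | 14 on 24–26; 13 on 24 |
| 30 | 24 | 4 on 29–30 | 14 on 24–26; 13 on 24 |
| 31 | 25 | 4 on 29–31 | 14 on 25–26 |
| 32 | 26 | 4 on 29–32 | 14 on 26 |
| 33 | 27 | 4 on 29–33 | none |
| 34 | 28 | 4 on 29–34 | none |
| 35 | 28 | 4 on 29–35 | none |

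The two limits fail by different routes. A late day 1 produces the lower-limit failures. Missed diary days produce the failures at 15, and a longer phase works against them (14 × 28/35 = 11.2 with a full diary).

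**How many.** The documents give neither the baseline distribution nor the timing of day 1. A simulation of migraine days assumed a mean of 7 to 9 days per 28 (SD 3) and 90 to 100% diary completion. The share of eligible subjects falling outside the SAP limits was:
- day 1 spread evenly over 28 to 35 days: about 3 to 9%;
- half the subjects at exactly 28 days: about 2 to 5%;
- all at 28 days: about 0 to 3%, all at the upper limit.

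The top of the range is 0.09 × 459 ≈ 41 subjects. Headache days were not simulated and could add some at the limit of 15. A cruder check of the lower limit alone takes 5 to 15% of subjects with exactly 4 days, and 10 to 50% with more than 28 diary days. That gives 459 × 0.05 × 0.10 = 2.3 to 459 × 0.15 × 0.50 = 34.4 subjects.

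**The case against.** The best objection is that the entry calculation is not visible. Criteria 106 and 107 rest on what the eDiary computes, and Protocol 7.2.13 leaves the details to the eDiary manual. Several hints point to 28 days: the phase is called a 4-week phase, the compliance example is out of 28, the Protocol glossary defines monthly migraine days as "Number of migraine days in any 28-consecutive day interval relative to study day 1", and Protocol 10.1.1.5 itself prorates to 28 days. If the device normalises over the same days, the conflict disappears. This stands, and it makes the finding conditional.

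Second, SAP 7.5 draws its items from an external deviation list, and SAP 10.3 takes eligibility deviations from the protocol, so the items might be judged on the eligibility result. That is possible, but 7.5 does not say so, and its wording matches the term defined in 6.1.1. The SAP does use the eligibility report to bound the baseline for symptom interference, bed days and missed work or school, but not for migraine or headache days.

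Third, proration sits under missing data, so a fully completed 35-day baseline might not be scaled at all. The text of 9.3 covers every interval with 14 or more diary days, but it is not explicit on this case. If such intervals are left unscaled, the lower-limit failures with full diaries go away and the failures at 15 remain.

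A reader might also infer that the primary analysis admits subjects below the entry floor, or that the treatment comparison is biased. The documents do not support either. On the literal reading these subjects do meet criterion 106. The primary analysis uses the Efficacy Analysis Set (SAP 7.2 and 10.5). The exclusion depends only on data from before randomised treatment, so it applies alike in all arms.

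**Conclusion.** The concern holds as a conditional inconsistency. If the eDiary reports an unprorated count and SAP 7.5 is programmed on its defined terms, some subjects who met entry are classed as important deviators. They are those with exactly 4 migraine days on 29 to 35 diary days, those with 14 migraine or headache days on 26 or fewer, and those with 13 on 24 or fewer.

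The effect is confined to the per-protocol sensitivity analyses of the primary and secondary endpoints. Its size, about 0 to 9% of subjects, rests on assumed frequencies, visit timing and completion. A reader might take the top of that range as an expected loss, or take the 28 to 35 day window as the cause at both limits. Neither follows: the first rests on day 1 being spread evenly over the window, and the window breaks only the lower migraine limit.

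**What to change.** In SAP 7.5, judge the two baseline-frequency items on the eDiary eligibility-report values used for criteria 106 and 107 at randomisation, not on the prorated analysis baseline. For example: *eligibility-report migraine days below 4 or at least 15; eligibility-report headache days at least 15*. This agrees with SAP 10.3. Add one sentence to the SAP saying whether the report value is a raw count or a 28-day equivalent. Settle both before unblinding.

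Leave criteria 106 and 107 unchanged. It is tempting to rewrite them, since 15 days in a full 35-day phase is only 15 × 28/35 = 12.0 per 28 days yet fails a raw limit of 15. But that changes who may enter, and Amendment 2 already provides for subjects past week 48, so it could leave subjects enrolled under two rules.

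The cost is the wording of two bullets, one added sentence and a look at the eDiary specification. The downside is small: a few subjects whose prorated baseline lies just outside 4 to <15 stay in the Per Protocol Set. If the device already normalises to 28 days, the change does no harm.
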